Anaphylaxis			Symptomatic bronchospasm, with or without urticaria; Parenteral intervention indicated; Allergy-related edema/angioedema; Hypotension	Life-threatening consequences; Urgent intervention indicated	Death
Hypotension			SBP < 90 mm hg or DBP < 50 mm hg	Requiring vasopressor support	Death
ALT (U/L)	Baseline-1.5x baseline	>200 and > 1.5x baseline	>400 and > 2x baseline	401-800 and > 3x baseline	>800
AST (U/L)	Baseline-1.5x baseline	>200 and > 1.5x baseline	>400 and > 2x baseline	401-800 and > 3x baseline	>800
Total Bilirubin (mg/dL)	0.1 to 1	1.1 to 2 and direct bilirubin >0.5	2 to 5 and direct bilirubin > 1	5.1 to 10	>10
Potassium (mg/dL)	5.1-5.3	> 5.3-5.5	> 5.5- 6.0 Investigator can assess for possible hemolysis	> 6.0	Death
Creatinine (mg/dL)	Creatinine level increase of >0.3 mg/dL; Creatinine 1- 1.5 x above baseline	Creatinine 1.5 - 2x above baseline	Creatinine >2x baseline or >2.0 mg/dL; Hospitalization indicated	Life-threatening consequences; Dialysis indicated	Death

Table 2. Scoring of toxicity for dose modification. Scoring of toxicity from the CTC Version 4.0, with modifications is proposed given the short duration of therapy and consideration of signs and symptoms

related to COVID-19 infection. Due to the nature of the trial and to minimize exposure to SARS-CoV2 monitoring laboratory assessments while on study drug/placebo will only occur in hospitalized patients. Grade 3, 4, 5 reactions warrant drug/placebo discontinuation

The risks and discomforts of frequent phlebotomy

Blood samples will be obtained to document changes in levels of biochemical markers of the RAAS system and to monitor the metabolic effects and toxicities of ramipril. Blood collection by venipuncture is associated with mild discomfort, and the possibility of localized bruising, phlebitis, or extravasation. The risk of infection or fainting is extremely small.

Data and Safety Monitoring

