The UC San Diego Clinical and Translational Research Institute will appoint an independent data safety monitoring board (DSMB) composed of two independent physicians and one statistician. The DSMB will undertake a review of the interim data from the study to ensure the safety of study participants and to recommend changes to the study including early termination or modification of the study if it appears futile. The DSMB will review a summary of data by randomized treatment arm for the primary outcome, toxicity and adverse events. A planned interim analysis will occur after approximately 50% of the planned enrollment from the trial has been completed, approximately 280 patients.

The principal investigator and research coordinator of this protocol will monitor data and safety regularly at weekly meetings. These meetings are separate from regular clinical rounds and consist of review of all study patients including flow sheets of major safety and efficacy measurements. All measurements and tests are well established in clinical medicine. Yearly reports are made to the UCSD IRB regarding safety and efficacy.

Adverse Event Reporting

All serious adverse events will be reported to the local IRB and sponsor within 7 days. Unexpected and related fatal or life-threatening events will be reported within 48 hours and reports will be sent to the FDA, MEDWATCH program (telephone [name]; or via the Internet at www.fda.gov/medwatch/index.html.)

Patient Privacy

All data and study forms will be in secured locations (locked room or cabinet) and access is limited to study personnel. Subject names are not used; instead a name code is assigned upon enrollment. Release of data to persons or organizations outside study personnel will require written consent of the subject.

All consents will be stored in well-marked binders in locked file cabinets located in private offices at UCSD Medical center. Databases with identifying information will be secure as they will be password protected and encrypted. Staff will be trained in HIPPA guidelines and confidentiality issues.

STATISTICAL METHODS AND CONSIDERATIONS

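### Table 2: the ALT, AST and bilirubin grades overlap, leave values ungraded and give Grade 5 a second meaning, so recorded severity labels are ambiguous

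*Combined protocol and SAP*

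**What the plan says.** Table 2 grades ALT and AST identically, in U/L:

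- Grade 1: "Baseline-1.5x baseline"
- Grade 2: ">200 and > 1.5x baseline"
- Grade 3: ">400 and > 2x baseline"
- Grade 4: "401-800 and > 3x baseline"
- Grade 5: above 800

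Total bilirubin, in mg/dL, is graded:

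- Grade 1: 0.1 to 1
- Grade 2: "1.1 to 2 and direct bilirubin >0.5"
- Grade 3: "2 to 5 and direct bilirubin > 1"
- Grade 4: 5.1 to 10, with no condition on direct bilirubin
- Grade 5: above 10

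In the other five rows (allergic reaction, anaphylaxis, hypotension, potassium, creatinine) Grade 5 is Death. The note under the table gives the source: "Scoring of toxicity from the CTC Version 4.0, with modifications is proposed".

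The grades are used in three places. Under Criteria for discontinuation and in the note to Table 2, Grade 3 or higher stops study drug. Under Adverse Events and Study Monitoring, an event goes on the case report form within 72 hours if it is Grade 3 or higher or leads to stopping. Under Data and Safety Monitoring: "The DSMB will review a summary of data by randomized treatment arm for the primary outcome, toxicity and adverse events". No section says that the highest grade met is the one recorded, and none fixes the layout of the DSMB summary.

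**The concern.** A severity scale should give each value exactly one grade, and each grade number one meaning. The liver rows do neither. Two sites with the same ALT result could record different grades and both be following the table. Some bilirubin values next to the stopping threshold have no grade, so the table does not say how the stopping and recording rules apply to them. Grade 5 marks a laboratory result in three rows and a death in five, so a count of Grade 5 events across rows would mix the two. What is at stake is the meaning of the Grade 3, 4 and 5 labels in the safety data, and consistent use of the bilirubin row by sites.

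**Working it through.** The plan states no figure to reproduce. The check applies the row definitions literally. Let v be the on-treatment ALT or AST and B the baseline, both in U/L. The documents give no baseline values; they exclude only ALT or AST above 5 times the upper limit of normal and do not state that limit. Baselines of 20 to 200 are therefore assumed.

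**1. ALT/AST overlap.** If v is 401 to 800 and v > 3B, then v > 400 and v > 2B, so every Grade 4 value is also Grade 3. If v > 400 and v > 2B, then v > 200 and v > 1.5B, so every Grade 3 value is also Grade 2. At B = 30, values of 401 to 800 meet Grades 2, 3 and 4, and values above 800 meet Grades 2, 3 and 5.

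A highest-grade convention would not be enough. For whole-number results, Grade 4 covers all of 401 to 800 whenever 3B < 401. That holds for B up to 133 (3 × 133 = 399), and Grade 3 is then never the highest grade met.

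**2. ALT/AST gap.** No grade applies when 1.5B < v ≤ 200. The gap exists only if B < 200/1.5 = 133.3.

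| Assumed B | 1.5B | Values with no grade | Highest grade met, 401 to 800 |
|---|---|---|---|
| 20 | 30 | 31–200 | 4 throughout |
| 30 | 45 | 46–200 (200/30 = 6.7 times baseline) | 4 throughout |
| 40 | 60 | 61–200 | 4 throughout |
| 100 | 150 | 151–200 | 4 throughout |
| 200 | 300 | none | 3 for 401–600, 4 for 601–800 |

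**3. Bilirubin.**

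| Total (mg/dL) | Direct (mg/dL) | Grades met |
|---|---|---|
| 1.5 | 0.3 | none |
| 2.0 | 1.1 | 2 and 3 |
| 3.0 | 0.8 | none |
| 3.0 | 1.2 | 3 |
| 5.0 | 0.8 | none |
| 5.1 | 0.8 | 4 |
| 10.1 | 5 | 5 |

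Total bilirubin above 2 and up to 5 with direct at or below 1 has no grade, so this row triggers neither stopping nor recording. At 5.1 with the same direct value, both are triggered. Results between 1.0 and 1.1, or between 5.0 and 5.1, are also ungraded, but only if reported to more than one decimal.

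**4. Effect on decisions.** Stopping and case report form entry both turn on meeting Grade 3 or higher. An ALT/AST value that meets Grades 3 and 4, or 3 and 5, triggers both under either label. A value that meets Grades 2 and 3 also triggers both if the rule is read literally, since Grade 3 is met. The ALT/AST gap ends at 200, below the Grade 3 floor of 400, so it triggers neither. With results to one decimal, the bilirubin band above 2 to 5 is the only gap that touches the stopping threshold.

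**5. Grade 5.** A living patient with ALT or AST above 800, or bilirubin above 10, is Grade 5 by the table. Potassium and creatinine are laboratory rows too and use Death, so a split between laboratory and clinical rows does not explain the difference.

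**The case against.** The strongest reply is that the table exists to decide discontinuation and that it mostly does so. Grades 3, 4 and 5 have the same consequence, the ALT/AST gap lies where no action is required, and the scale is declared to be a modified one. The trial is double-blind, so any ambiguity falls on both arms under the same rule, and no bias between arms is shown. The note to Table 2 also limits laboratory monitoring on study drug to hospitalized patients. All of this stands, and it limits the point. It does not explain values with two grades or none, or one grade number with two meanings: a declared modification accounts for changed cut-offs only. The direct-bilirubin condition may be a deliberate exemption, but the documents do not say so, and the condition disappears at 5.1.

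Three stronger readings are tempting, and the documents do not support them.

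- *Living patients would be counted as fatal.* The liver cells do not say death, mortality is collected as a component of the primary outcome, and no DSMB layout by grade is specified. The error arises only if grades are pooled across rows and Grade 5 is read as death.
- *Expedited reporting would be distorted.* Adverse Event Reporting relies on events being serious, unexpected, related, fatal or life-threatening. It does not refer to Table 2 grades.
- *Unchanged values would fill the by-arm tables as Grade 1.* An unchanged ALT does fall in Grade 1, but case report form entry is required only for Grade 3 or higher or for events that lead to stopping.

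**Conclusion.** The point holds as a minor inconsistency in the safety grading. As written, the ALT, AST and bilirubin rows are not a usable severity scale: grades are nested, some values have none, and Grade 5 has two meanings. In practice, the Grade 3, 4 and 5 labels on the case report form are ambiguous for ALT/AST; the bilirubin row is silent over part of the range next to the stopping threshold; and a living patient could appear as Grade 5 if the DSMB toxicity summary is tabulated by grade across rows. The ALT/AST overlap does not alter who stops drug or whose event is recorded.

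The width of the ALT/AST gap depends on the assumed baseline, from 31 to 200 U/L at a baseline of 20 to no gap at 200. The overlap and the double meaning of Grade 5 follow from the table alone. The number of patients affected cannot be estimated, because the documents give no expected frequency of such results. The primary efficacy analysis is not touched.

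**What to change.** Reconcile the ALT, AST and bilirubin rows with the rest of Table 2 so that each value meets one grade, adjacent grades join without gaps, and Grade 5 has one meaning. State explicitly how total bilirubin above 2 and up to 5 mg/dL with direct bilirubin at or below 1 is to be handled, so that its position relative to the stopping rule is clear. The cut-offs and the stopping rule are for the clinical team; none is proposed here.

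In the DSMB tables, report deaths separately from laboratory grades, and show laboratory grades by row rather than pooled. Liver events already recorded can be regraded from the underlying values where these were kept.

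The cost is a correction to one table, matching edit checks on the case report form and a note on the DSMB table layout. Sample size, visits and the primary analysis do not change.

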(For discharged to outpatient sub-group only) Need for hospitalization

Proportion of patients developing hypotension and needing pressor support

Proportion of patients developing septic shock defined as sepsis with hypotension requiring vasopressors to maintain MAP \geq 65 and serum lactate > 2 mmol/L after fluid resuscitation (Sepsis-3 JAMA 2016)

Acute kidney injury defined by KDIGO guidelines, increase in serum creatinine by ≥ 0.3 mg/dL within 24 hours or increase in serum creatinine ≥ 1.5 times baseline.

Composite of mortality or need for ICU admission or invasive mechanical ventilator use within a 28-day window

Exploratory objective:

To examine the efficacy of ramipril in improving biomarkers of the renin-angiotension-aldosterone axis

To examine racial differences in response to treatment with ramipril in patients with COVID-19 infection

Primary outcome measure:

Composite outcome includes mortality (yes/no) or need for ICU admission or invasive mechanical ventilation (yes/no) at 14-day from the start of treatment (or at any point within the 14-day window).

Secondary outcomes:

1. Proportion of patients needing continued hospitalization at day 14
2. Time to discharge from the hospital
3. (For outpatient sub-group only) Need for hospitalization
4. Proportion of patients developing hypotension and needing pressor support
5. Proportion of patients developing septic shock
6. Proportion of patients developing acute kidney injury
7. Composite of mortality or need for ICU admission or invasive mechanical ventilator use within a 28-day window

STUDY DESIGN

This is a randomized, double-blinded, placebo-controlled clinical trial to examine the efficacy of ramipril at 2.5 mg orally daily versus placebo given over 14 days to improve outcomes in patients with documented COVID-19 infection. 560 subjects will be randomized, monitored at regular intervals for the 14 days, and will be invited to continue participating in the study for an additional 1 year for monitoring. Study participants and investigators will be blinded to study assignment.

Randomization

Randomization will occur in a 2:1 ratio to treatment and placebo study arms respectively using permuted block randomization by UCSD investigational drug services.

Recruitment

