Recruitment will occur through referral from patients presenting to the emergency department, urgent care, other ambulatory clinics or currently hospitalized. In addition, system lists generated to track patients undergoing testing for COVID-19 infection will be used for recruitment in accordance with the partial HIPAA waiver. Study sites will communicate study availability to their emergency departments, urgent care, other ambulatory clinics and hospital wards. Given the scope of the pandemic and lack of effective therapies we anticipate rapid study accrual.

Study Visits

All subjects: Study visits will occur virtually and in accordance with IRB guidelines to reduce the risk of SARS-CoV-2 transmission and preserve personal protective equipment. Informed consent will be obtained by study personnel by videoconference or telephone. A HIPAA waiver will be completed by study subjects so that study personnel can extract relevant data from the medical record. Subjects may be asked to provide copies of their COVID-19 test results, medical history, imaging results and concomitant medications. Subsequent study visits will occur by videoconference or telephone.

Inpatients only: Regular laboratory assessment will be extracted from the medical record on inpatients.

Discharged to outpatient only: A mobile phlebotomy unit maybe used for blood draws for outpatient subjects (Sites will seek approval from UCSD prior to use of third party vendor for mobile phlebotomy services). Patients discharged from the hospital at any point after randomization will receive sufficient drug/placebo to complete the study and will continue to be monitored by videoconference or telephone and will follow up for end of treatment (EOT)/Day 14.

SUBJECT SELECTION

Inclusion Criteria:

- Age \geq 18 years
- Willing and able to provide written informed consent prior to performing study procedures OR legally authorized representative has been fully informed and has given voluntary written informed consent in compliance with local regulations.
- Severe Acute Respiratory Syndrome Coronavirus (SARS-CoV)-2 infection confirmed by polymerase chain reaction (PCR) test \leq 7 days before randomization
OR
Clinical presentation consistent with COVID-19 infection (fever or cough or shortness of breath) with positive IgM serology

Exclusion Criteria:

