¹As outlined in study figure: Complete blood count with differential, comprehensive metabolic panel, oxygen saturation and confirmation of pregnancy status. These tests should be obtained through the study if not obtained for routine clinical care.

²Only required if greater than 24 from screening visit

⁴Laboratory assessment: Complete blood count with differential, comprehensive metabolic panel.

Premature Discontinuation of Study Drug

Patients meeting a primary endpoint for the study defined as invasive mechanical ventilation or transfer to the intensive care unit or death will stop study drug/placebo. In addition, patients who discontinue due to toxicity rules defined below may stop the study drug/placebo. Additional data on secondary endpoints will continue to be collected and the SOE will be completed when possible.

Post-Treatment Phase:

At the end of the 14-day treatment phase, patients will be followed for another 14 days until day 28 and receive a phone visit to assess any changes in the clinical status related to primary and secondary outcomes. It is not possible to predict the outcome of this study, but if ramipril appears to have a significant effect on COVID-19 outcomes, we will likely develop a follow-up protocol to assess its impact on long-term virologic cure, immune function, lung function and long-term survival and re-infection due to COVID.

ADVERSE EVENTS AND STUDY MONITORING

Safety will be assessed on a continuous basis in the study. Adverse events are any unfavorable or unintended sign, symptom or diagnosis that occurs in a study participant during the conduct of the study independent of attribution. All adverse events will be recorded on case report forms within 72 hours if it meets any of the following criteria: \geq Grade 3 toxicity (per Table 2) or those that lead to cessation of study drug/placebo regardless of toxicity.

Risks and hazards of Ramipril:

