The primary outcome of this study will be represented by a composite of outcomes which will include mortality, ICU admission, and/or need for ventilator use within a 14-day period. Statistical analyses will compare outcomes between treatment versus placebo-arms. It is not possible to predict what the spontaneous or therapeutic response rate will be. Thus, we predict that the spontaneous improvement rate would be zero to less than 1%. In the primary analysis, we assume that the 14 day mortality/ICU admission/Ventilator use of placebo and ramipril-treatment group to be 22% and 12%, and the proportion of the sample from placebo to ramipril-treatment group to be 1:2. Therefore, using Whittemore's formula (Whittemore, 1981), we estimate a sample size of 510 patients--340 in the ramipril arm and 170 in the placebo arm—will be required to detect effects with a power 80% (or higher) with a Type I error rate of alpha = 0.05. This formula is used for logistic regression which has an overall event proportion of P and an odd ratio of r at one standard deviation above the mean of the predictor.

Statistical analysis plan:

The primary outcome will first be analyzed using a 2x2 contingency table (treatment by outcome) and testing will use Fisher's exact test. Primary analyses will be Intent to Treat (ITT).

We expect to enroll up to 560 patients in this study and randomize at least 510 of them to either treatment or placebo arm for a full 2 weeks with a follow-up evaluation. Therapeutic intervention trials have had variable dropout rates. Previous short-term studies of ramipril had less than 10 % dropouts. Therefore, we expect less than a 10% dropout rate. Dropouts would be considered non-responders based upon intention to treat analysis. A modified intention to treat analysis will be done in which we will exclude the patients who dropped out before getting the week 2 exit evaluation.

[figure not shown]
Primary and secondary outcomes will be assessed comparing placebo and treatment arms using parametric or non-parametric tests as indicated.

The major **primary outcome** to be evaluated is a composite of mortality or need for ICU admission or invasive mechanical ventilator use within a 14-day window.

The major **secondary outcomes** to be evaluated are:

1. Proportion of patients needing continued hospitalization at day 14
2. Time to discharge
3. (For discharged to outpatient sub-group only) Need for hospitalization

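### Secondary outcomes 1 and 2 have no rule for patients who die before discharge, and the population of outcome 3 is labelled in two ways

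*Combined protocol and SAP*

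**What the plan says.** The Secondary outcomes list and the Statistical analysis plan both give outcome 1 as "Proportion of patients needing continued hospitalization at day 14". Neither gives a denominator or a rule for deaths. Outcome 2 is time to discharge, with no definition of event or censoring. The only method text for the secondary outcomes is that they will be assessed "comparing placebo and treatment arms using parametric or non-parametric tests as indicated".

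Death is counted elsewhere. The primary outcome reads "Composite outcome includes mortality (yes/no) or need for ICU admission or invasive mechanical ventilation (yes/no) at 14-day from the start of treatment", and the section on premature discontinuation of study drug refers to "Patients meeting a primary endpoint for the study defined as invasive mechanical ventilation or transfer to the intensive care unit or death". Secondary outcome 7, the 28-day composite, also includes mortality. The one rule for incomplete follow-up is "Dropouts would be considered non-responders based upon intention to treat analysis"; it does not mention deaths.

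The population of outcome 3 is worded in two ways. The Secondary objectives and the Statistical analysis plan have "For discharged to outpatient sub-group only) Need for hospitalization". The Secondary outcomes list has "For outpatient sub-group only) Need for hospitalization". Under Study Visits, the paragraph on participants discharged to outpatient care says: "Patients discharged from the hospital at any point after randomization will receive sufficient drug/placebo to complete the study".

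**The concern.** A patient who dies on day 8 does not need a hospital bed on day 14. On a literal reading in all randomized patients, that death joins the patients who went home. An arm with fewer deaths then keeps more living patients who may still be in hospital, and can look worse for that reason. Excluding deaths does not solve this, because it compares survivors only, and survival is one of the things ramipril is meant to change.

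For time to discharge, an analyst could drop deaths, censor them at death, or hold them as never discharged. These estimate different quantities. With neither the rule nor the test fixed, the choice could be made after the data are seen.

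For outcome 3, if the subgroup is formed by discharge after randomization, treatment can affect who enters it, and the arms are no longer compared as randomized.

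Time to mortality is named as a secondary endpoint in the Abstract and Specific Aims but is missing from the later outcome lists. In those lists death appears only inside composites, so no listed mortality outcome stands beside outcomes 1 and 2 to correct a misleading picture.

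**Working it through.** **Inputs from the documents.** Composite event rates of 22% (placebo) and 12% (ramipril), with 170 and 340 patients, from Statistical Methods and Considerations. 28-day mortality of 9.8% (non-users) and 3.7% (users) in the retrospective cohort described in the Background. The plan states no figure for outcomes 1 to 3. Its 510 serves here only for arm sizes; at 22% and 12% it gives 82.3% power by the normal approximation and 80.7% by Fisher's exact test (two-sided 0.05), consistent with the plan's claim.

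**Outcome 1, assumption A: same share of survivors in hospital in both arms.** Let f be the share of composite events that are deaths (assumed 10%, 25%, 50%), so mortality m is 0.22f on placebo and 0.12f on ramipril. Let h be the share of survivors still in hospital (assumed 10%, 20%, 30%).

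- Literal: (1 - m)h
- Dead or still in hospital: m + (1 - m)h
- Standard error of a difference: sqrt(sum of p(1 - p)/n)

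Ramipril minus placebo, in percentage points:

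| h | f | Literal | Deaths counted |
|---|---|---|---|
| 10% | 10% | +0.10 | -0.90 |
| 10% | 25% | +0.25 | -2.25 |
| 10% | 50% | +0.50 | -4.50 |
| 20% | 10% | +0.20 | -0.80 |
| 20% | 25% | +0.50 | -2.00 |
| 20% | 50% | +1.00 | -4.00 |
| 30% | 10% | +0.30 | -0.70 |
| 30% | 25% | +0.75 | -1.75 |
| 30% | 50% | +1.50 | -3.50 |

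Worked case, h = 20% and f = 50%: mortality is 11.0% and 6.0%. Literal: 0.89 × 0.20 = 17.8% and 0.94 × 0.20 = 18.8%. With deaths counted: 28.8% and 24.8%. The sign reverses in all nine cases. The gap between the two scorings is (0.22 - 0.12)f, that is 1.0, 2.5 or 5.0 points whatever h is. The largest literal difference is 0.36 standard errors (1.5/4.18) and the largest with deaths counted is 1.24 (4.5/3.63). Excluding deaths gives h in both arms, a difference of 0.

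**Outcome 1, assumption B: same share discharged alive in both arms.** Take 70% discharged alive by day 14 in each arm (assumed), and apply the 28-day deaths of 9.8% and 3.7% to day 14 (assumed).

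- Literal: 30 - 9.8 = 20.2% on placebo and 30 - 3.7 = 26.3% on ramipril, so +6.1 points. Fisher's test rejects in about 31% of such trials, against about 4.5% when both arms are at 30%.
- Excluding deaths: 20.2/90.2 = 22.4% and 26.3/96.3 = 27.3%, so +4.9 points.
- Deaths counted: 30% and 30%, a difference of 0.

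With equal deaths of 5%, all three scorings give no difference.

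**Outcome 2.** Assume a discharge hazard of 0.10 per day in both arms and death hazards of 0.010 (placebo) and 0.004 (ramipril), followed to day 28.

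- Deaths censored: 1 - exp(-0.10 × 28) = 93.9% discharged in both arms.
- Deaths held as never discharged: [0.10/(0.10 + d)] × [1 - exp(-(0.10 + d) × 28)], where d is the death hazard, gives 86.7% on placebo and 90.9% on ramipril.

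With a rank test and identical discharge times in survivors, the probability that a ramipril patient ranks better is 0.500 if deaths are dropped and 0.5 + (0.22f - 0.12f)/2 if they are ranked last: 0.505, 0.5125 and 0.525 for the three values of f. The standard error is sqrt(511/(12 × 170 × 340)) = 0.027, so the largest shift is 0.92 standard errors.

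**Outcome 3, if it means patients discharged after randomization.** Assume 80% discharged on placebo and 85% on ramipril. Give the common 80% a readmission risk of 10% and the extra 5% a risk x of 10%, 20% or 30%. The ramipril rate is (0.80 × 0.10 + 0.05x)/0.85 = 10.0%, 10.6% or 11.2%, against 10.0%. With 136 and 289 patients, that is a shift of 0 to 1.2 points, at most 0.37 standard errors, with no treatment effect on readmission.

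**The case against.** Four counter-arguments deserve weight.

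- **An omission is not a scoring rule.** A reader might infer that the plan prescribes counting deaths as favourable. It does not: no denominator is given, and excluding deaths is also a possible reading. This stands. The supportable claim is that no rule exists and that both readings can mislead.
- **The effect is small and rests on assumptions.** Under assumption A the literal difference stays within 0.36 standard errors, so the test result would rarely change. Assumption B gives a larger figure only because it fixes a different unknown. This also stands: neither input is in the documents, and the size cannot be settled from them.
- **Death is not lost.** It is in the primary outcome and in outcome 7. This is correct and limits the consequence to the secondary outcomes.
- **The preferred analyses are partly a choice of estimand.** Censoring at death describes the discharge rate among patients still at risk, which is a legitimate quantity, and deaths could be shown beside an unchanged outcome 1. That is fair, but the plan still has to choose, and it has not.

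The dropout rule might be thought to cover deaths. The documents treat death as an endpoint, and the rule does not say what a non-responder is for outcomes 1 or 2. If deaths were taken as dropouts, the modified intention-to-treat analysis would exclude those occurring before the week 2 evaluation.

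It is also tempting to read outcome 3 as certainly a subgroup formed after randomization. The Treatment section uses the two labels for the same patients, which favours that reading. But Recruitment includes ambulatory clinics, so participants who were never admitted remain possible.

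**Conclusion.** The concern holds as a gap in definition. Outcomes 1 and 2 have no rule for deaths, outcome 2 has no named test, and the outcome 3 labels conflict. If mortality is equal between arms, outcomes 1 and 2 are little affected. If it differs, the direction of outcome 1 can depend on the scoring: +0.1 to +1.5 points literal against -0.7 to -4.5 with deaths counted under assumption A, and +6.1 against 0 under assumption B. All of these rest on assumed death shares and discharge patterns, and assumption B also moves 28-day mortality to day 14.

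A reader might go further and infer that the trial's main result is compromised. The documents do not support that, since the primary outcome and the 28-day composite include death. For outcome 3, the loss of a randomized comparison on one reading matters more than the size of the shift. This is a cheap improvement to secondary outcomes.

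**What to change.** Before unblinding:

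- **Outcome 1.** Among patients in hospital at randomization, define it as dead or still hospitalized at day 14, and show deaths separately beside it.
- **Outcome 2.** Analyse time to discharge alive to day 28, with deaths held as never discharged. Use cumulative incidence with Gray's test, or a rank test with deaths ranked last, and name which.
- **Deaths and dropouts.** State that a death is an outcome and not a dropout.
- **Never-admitted patients.** The Hypothesis concerns hospitalized patients while Recruitment is wider, so state how any such patient counts in outcomes 1 and 2.
- **Outcome 3.** Reconcile the population between the Secondary objectives, the Secondary outcomes list and the Statistical analysis plan. If it is patients discharged after randomization, report it descriptively, or at least not as a randomized comparison.

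No new data are needed, since vital status and discharge date are already required for the listed outcomes. These are changes of definition, however: outcome 1 becomes a further composite that partly overlaps with the primary outcome, and outcome 3 may no longer be a tested comparison.
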